5.2 Phase B Analysis

Phase B endpoints will be analyzed in a similar fashion as Phase A endpoints. This analysis plan is only focused on Phase B analysis.

6 SAMPLE SIZE DETERMINATION

The sample size for this trial was based upon accepted investigational studies exploring changes in bone density.

Based upon the subchondral BMD data obtained using qCT in SM04690-01, a coefficient of variation (CV) of 0.30 was presumed to be shared by both treatment and placebo groups; this presumed CV is larger than the observed CVs in SM04690-01. Assuming a Type 1 error of 0.05, 100 subjects (50 subjects per group) will provide 81.6% power to estimate a BMD ratio (SM04690 : placebo) of 0.93 with a one-sided confidence interval extending to 0.80 assuming a non-inferiority design.

7 ANALYSIS POPULATIONS

7.1 Full Analysis Set

The Full Analysis Set (FAS) includes all subjects who were randomized and received at least one study injection. The FAS is used to describe the analysis set which is as complete as possible and as close as possible to the intent-to-treat ideal of including all randomized subjects. Subjects will be analyzed as randomized for the FAS.

7.2 Full Analysis Set Phase B

The Full Analysis Set Phase B (FASB) includes all FAS subjects who received at least one study injection in Phase B. Subjects will be analyzed as randomized for the FASB.

7.3 Modified Full Analysis Set

The modified Full Analysis Set (mFAS) includes all FAS subjects who received both scheduled Phase A injections into the target knee (Day 1, Week 24). Subjects will be analyzed as randomized for the mFAS.

7.4 Per-Protocol Analysis Set

The Per-Protocol Analysis Set (PPAS) includes all mFAS subjects who completed Phase A of the study (i.e. subjects who terminate the study early will be excluded) and did not have any protocol deviations that may have impacted the evaluation of efficacy outcomes (see [Section 9.2](#)). Subjects will be analyzed as randomized for the PPAS. A list of subjects excluded from PPAS can be found in the Phase A SAP.

7.5 Per-Protocol Analysis Set Phase B

The Per-Protocol Analysis Set Phase B (PPASB) includes all PPAS who completed Phase B of the study and did not have any protocol deviations in Phase B that may have impacted the evaluation of efficacy outcomes (see [Section 9.2](#)). Subjects excluded from per-protocol analysis in Phase A are by definition excluded from per-protocol analysis in Phase B. Subjects will be analyzed as randomized for the PPASB.

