5.5.2 HANDLING OF PARTICIPANT WITHDRAWALS OR TERMINATION

In case of premature discontinuation of study participation, ET procedures should be conducted within 14 days of discontinuation for any subject who discontinues after the Day 1 visit, if possible. The date the subject is withdrawn from the study and the reason for the discontinuation should be recorded on the eCRF. The Investigator or designee must complete all applicable eCRF pages for subjects who discontinue from the study prematurely.

Replacement of subjects who withdraw or discontinue prematurely is not allowed.

Subjects who are withdrawn from study medication for safety reasons will continue with all planned study visits per protocol, without any further dosing.

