6.1.9 DURATION OF THERAPY

The injectable investigational product or placebo is to be administered as a single intra-articular injection into the target knee joint once each at Day 1 and Week 24 (Phase A), and once each at Week 52 (EOSa) and Week 76 (Phase B).

At the Week 24, 52 (EOSa), and 76 visits, the Investigator should evaluate the subject for suitability to receive the study medication injection. The subject should not have any condition, including laboratory findings and findings in pre-injection assessments, that, in the opinion of the Investigator, constitutes a risk or contraindication for the injection, or that could interfere with the study objectives, conduct, or evaluation. The injections may occur up to two weeks later than the Week 24, 52 (EOSa), and 76 visits, respectively, to allow for resolution of any intercurrent illness (e.g., infection) prior to the injection. If, in the opinion of the Investigator, the subject should not receive any of the injections, the subject will discontinue treatment but will continue with all planned study visits per protocol.

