9.2 Protocol Deviations

A protocol deviation is defined as any noncompliance with the clinical trial protocol requirements. The noncompliance may be either on the part of the subject, the Investigator, or the study site staff.

Deviations are summarized into one of the following categories:

- Investigational Product
- Informed Consent
- Enrollment
- Procedures
- Labs/Specimens
- Study Visits
- Source Documentation

- Diaries, Questionnaires, or Patient Reported Outcomes
- Subject Non-Compliance
- Serious Adverse Events

Deviations are categorized as major or minor by a cross-functional team according to pre-defined criteria established in the Protocol Deviation Classification Guideline.

- A major deviation is defined as a divergence from the protocol that materially (a) reduces the quality or completeness of efficacy data, (b) makes the informed consent inaccurate, or (c) impacts a subject's safety, rights or welfare.
- A minor deviation is defined as a divergence from the protocol that deviates from the procedures and guidelines outlined in the protocol, but is not classified as a major deviation (i.e. the deviation does not materially (a) reduce the quality or completeness of the data, (b) make the informed consent inaccurate, or (c) impact a subject's safety, rights or welfare).

Protocol deviations may result in subject exclusion from the PPASB. Prior to Phase B database lock, all protocol deviations were reviewed by study team members to determine if the deviation could reasonably affect/confound interpretation of efficacy endpoints and should result in the subject being excluded from the PPASB. Subjects with the following types of deviations were excluded from the PPASB:

- Subjects taking pain medications that may significantly impact pain and function assessment

A final list of protocol deviations resulting in subject exclusion from the PPAS and PPASB can be found in [Appendix 2](#).

Major protocol deviations that occurred in Phase B will be summarized by site and category, and all protocol deviations will be listed for each subject. Additionally, the COVID-19 pandemic related protocol deviations that occurred in Phase B will be summarized separately.

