14.2 Exposure

All treated subjects were scheduled to receive two injections during Phase A of the trial and two injections during Phase B of the trial. A summary table of the number injections received will be provided. A list of lot numbers used in this study will be provided in the clinical study report.

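### The Phase B per-protocol set has no dosing condition, so a subject whose Week 52 or Week 76 injection is withheld under the protocol can still qualify as per-protocol

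*SAP*

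**What the plan says.** **Phase A.** SAP 7.4 builds the per-protocol set (PPAS) on the modified full analysis set: it "includes all mFAS subjects who completed Phase A of the study" and had no deviation that may have affected the efficacy evaluation. SAP 7.3 says the mFAS "includes all FAS subjects who received both scheduled Phase A injections into the target knee (Day 1, Week 24"). Dosing is therefore a condition of the PPAS by inheritance.

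**Phase B.** SAP 7.5 says the PPASB "includes all PPAS who completed Phase B of the study and did not have any protocol deviations in Phase B". The sentence goes on to limit this to deviations that may have affected efficacy evaluation, and points to SAP 9.2. The Phase B full analysis set (FASB) "includes all FAS subjects who received at least one study injection in Phase B" (SAP 7.2). SAP 14.2 gives the planned exposure: "All treated subjects were scheduled to receive two injections during Phase A of the trial and two injections during Phase B of the trial".

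**Deviations.** SAP 9.2 defines a deviation as noncompliance with the protocol. All deviations were reviewed before the Phase B lock for their possible effect on efficacy interpretation. The categories include one for investigational product and one for subject non-compliance. One type is listed as leading to exclusion from the PPASB: "Subjects taking pain medications that may significantly impact pain and function assessment".

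**Withheld injections.** Under protocol 6.1.9, if the Investigator judges that an injection should not be given, "the subject will discontinue treatment but will continue with all planned study visits per protocol". Protocol 5.5.2 adds: "Subjects who are withdrawn from study medication for safety reasons will continue with all planned study visits per protocol, without any further dosing".

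**Use of the set.** SAP 12 uses the PPASB, alongside the FASB, for the Pain NRS descriptive summary and the Pain NRS MMRM through Week 104. SAP 9.3 uses both sets for the baseline tables.

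**The concern.** The two per-protocol sets carry the same label but different content. In Phase A, membership means that both planned injections were given. In Phase B, it means that the subject stayed to the end without an excluding deviation, whatever was injected after Week 24.

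The Phase A condition was deliberate: the log for Amendment 01 records that the PPAS was moved from the FAS to the mFAS. Protocol 10.4.4 and SAP 5.2 both say Phase B follows the Phase A approach. SAP 15 lists one change to the planned analysis, the reference point for biomarker change, and does not mention dropping the dosing condition. The difference therefore looks unintended.

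The Pain NRS MMRM is the only efficacy model in the Phase B plan, and it is run on two sets. The FASB by design admits subjects with a single Phase B injection. If the PPASB can admit them too, neither run is restricted to subjects who had the full four-injection schedule, and a reader would assume that the per-protocol run is.

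**Working it through.** The plan gives no figure on this point. Its one power figure (81.6%, SAP 6) concerns the knee BMD ratio and has no bearing here. The check is to apply the definitions as written.

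**Step 1: does completing Phase B imply dosing?** No. SAP 7.4 explains completion of Phase A as not having left the study early, and brings dosing in separately through the mFAS. Protocol 6.1.9 and 5.5.2 keep undosed subjects in their planned visits. A subject can therefore reach Week 104 without a Phase B injection.

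**Step 2: does the deviation rule remove an undosed subject?** Not if the injection was withheld under 6.1.9. SAP 9.2 defines a deviation as noncompliance, and withholding under 6.1.9 is what the protocol provides for. A dose missed for another reason could be logged under the investigational-product or non-compliance category and considered in the review, but no stated rule turns it into an exclusion. In addition, for deviations tied to a visit, SAP 9.2 counts only those at Weeks 64, 76, 88 and 104 as Phase B. One logged at the Week 52 visit falls outside.

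**Step 3: apply the sets.** Take a PPAS subject who completes Phase B with no excluding deviation.

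| Week 52 | Week 76 | FASB (SAP 7.2) | PPASB as written (SAP 7.5) | PPASB with a Phase A-style rule |
|---|---|---|---|---|
| given | given | in | in | in |
| given | not given | in | in | out |
| not given | given | in | in | out |
| not given | not given | out | in | out |

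All four patterns meet the present wording; one of the four would meet a rule that mirrors Phase A. The last row also shows that the PPASB is not a subset of the FASB, because it is built on the PPAS.

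**Step 4: which rows can 6.1.9 produce?** Withholding ends treatment. Withholding at Week 76 gives row 2, and withholding at Week 52 gives row 4. Row 3 would need some other route.

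**Step 5: how much data does each such subject contribute?** The windows are in SAP Appendix 1.
- Row 2: Week 77 starts on Day 533 and Week 104 ends on Day 728, so (728 − 533 + 1) / 7 = 196 / 7 = 28 weekly averages follow the scheduled Week 76 injection.
- Row 4: Week 53 starts on Day 365, so (728 − 365 + 1) / 7 = 364 / 7 = 52 weekly averages follow the scheduled Week 52 injection.

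These are maximum counts per subject. They say nothing about how many subjects are affected.

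**The case against.** **The review in SAP 9.2 is broader than the one listed type.** It covered all deviations, and the pain-medication line is in the past tense, so it can be read as the outcome of the review and not as a limit on it. This stands. A reader might infer that anyone who skips Week 76 is counted as per-protocol; the documents do not support that. A non-compliant missed dose can be excluded. The definite gap is the compliant, withheld injection. For the rest, what is missing is a rule that requires exclusion.

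**Actual handling is not known.** SAP 9.2 refers to a final exclusion list in Appendix 2, which is not in the text available for this review. This also stands: the point concerns the written rule and is not a claim that any particular subject was wrongly included.

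**A subject handled under 6.1.9 has followed the protocol.** Counting that subject as per-protocol is a defensible use of the term, and the SAP does not state what the PPASB is meant to show. But the sponsor chose the other meaning for Phase A and said that Phase B would be analysed similarly. If the meaning was changed on purpose, the SAP should say so.

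**Dosing after randomisation is a selection.** Requiring the Week 76 injection selects on an event that may be linked to safety. That is true, and the Phase A PPAS already accepts it. The FASB remains as the fuller set.

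**Conclusion.** The concern holds as a gap in the definition. SAP 7.5 sets no Phase B dosing condition. A PPAS subject whose Week 52 or Week 76 injection is withheld under protocol 6.1.9, who attends to Week 104 and has no excluding deviation, meets the PPASB wording. With no Phase B injection, that subject meets it while failing the FASB.

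The size cannot be stated. The documents give no count of missed Phase B injections among PPAS subjects who completed, and the count may be zero. A reader might infer that the Week 104 per-protocol estimate is diluted in proportion to the share of SM04690 subjects who missed Week 76. That would need a share the documents do not give, and would also need the fourth injection to carry the whole Week 104 effect with nothing left from the first three. Nothing in the documents supports either, so no dilution figure should be attached.

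The reach is limited to the per-protocol Pain NRS summary and MMRM and the per-protocol baseline tables. The FASB results are unaffected. Phase A is the primary analysis, protocol 10.2 plans no formal hypothesis test, and SAP 12 provides no estimands for Phase B. The correction is still worth making: it is cheap, and without it the per-protocol label means different things in the two phases.

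**What to change.** In SAP 7.5, define the PPASB as PPAS subjects who received both scheduled Phase B injections into the target knee (Week 52 and Week 76), completed Phase B, and had no Phase B deviation that may have affected the evaluation of efficacy. Apply the injection condition by program from the dosing records. This matches the mFAS condition in Phase A and makes the PPASB a subset of the FASB. It also takes the dosing question out of case-by-case review, which is useful because the sponsor was unblinded after the Phase A analysis (SAP 4.3) and SAP 9.2 does not say that the reviewers were kept blind.

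If the set is already locked, leave it as it is. Report by treatment group how many PPASB subjects missed either injection, and rerun the Pain NRS MMRM without them as a documented addendum. The exposure table planned in SAP 14.2 already needs the dosing data.

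The cost is one sentence and one programming condition, or one extra model run. The set may become slightly smaller and is selected on a post-randomisation event, as the Phase A PPAS already is. The FASB does not change.

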7.6 Safety Analysis Set

The Safety Analysis Set (SAS) includes all subjects who received at least one study injection. Subjects will be analyzed as treated on Day 1 for the SAS. In this study, the FAS and SAS are identical, but for consistency with other studies, the SAS will be used in summaries of safety.

7.7 Safety Analysis Set Phase B

The Safety Analysis Set Phase B (SASB) includes all subjects who received at least one study injection in Phase B. Subjects will be analyzed as treated on Day 1 for the SASB. In this study,

the FASB and SASB are identical, but for consistency with other studies, the SASB will be used in summaries of safety.

8 GENERAL ISSUES FOR STATISTICAL ANALYSIS

8.1 General Statistical Methodology

For continuous variables, the outcome measure at each visit, as well as the absolute change (outcome at visit – outcome at baseline), will be summarized within each treatment group using descriptive statistics (number of subjects, mean, standard deviation (SD), median, minimum, and maximum). The number of evaluable subjects in any analysis set may vary by endpoint/timepoint based on missing data. Categorical variables will be summarized with frequency tables.

All subject-level listings will be comprehensive and include subjects enrolled in both Phase A and Phase B. Data collected from unscheduled visits will not be included in summary tables but will be included in subject-level listings as appropriate.

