7. STUDY PROCEDURES AND SCHEDULE

7.1 STUDY PROCEDURES/EVALUATIONS

7.1.1 STUDY SPECIFIC PROCEDURES

Collection of Adverse Events Data

Data regarding AEs will be collected in this study. AEs are events that occur during the course of the study that are not present prior to Day 1 study medication injection, or, if present at the time of study medication injection, have worsened in severity during the course of the study. AEs will be assessed at each study visit from the time of study medication injection on study visit Day 1 through the subject's last study visit.

Each subject will be observed and queried by the Investigator or the Investigator's designee at each study visit for any continuing AEs or new AEs since the previous visit. The subject may be asked to return to the site for an unscheduled visit if an AE occurs between study visits, and if, in the opinion of the Investigator, the AE requires a study visit for full evaluation. Any AE reported by the subject or noted by the Investigator or the Investigator's designee will be recorded within the eCRF. The following information will be recorded for each AE: description of the event, date of onset and resolution, etiology, and severity as assessed by the Investigator according to the Clinical Data Interchange Standards Consortium (CDISC) Severity/Intensity Scale for Adverse Events (AESEV) ([Table 1](#)), causal relationship to study medication, outcome, and any treatment given.

In this protocol, signs and symptoms of exacerbation or worsening of target knee OA will be captured in the context of efficacy assessments and recorded on specific pages of the eCRF.

Anticipated fluctuations or anticipated deterioration (in the opinion of the Investigator) of the underlying disease (target knee OA) will not be considered as AEs nor captured on the AE page of the eCRF.

Whenever possible, it is preferable to record a diagnosis as the AE term rather than a series of symptoms relating to a diagnosis. Fluctuations of pre-existing conditions, including the disease under study, that do not represent a clinically significant exacerbation or worsening, need not be considered AEs.

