7.3.3 FOLLOW-UP

Week 4

The Week 4 visit should occur on Day 29 (with a window of + 3 days). Subjects should fast for 8 hours prior to this visit.

The following procedures and assessments will be performed at this visit:

- Collection of AE and concomitant procedures/medication data
- Physical examination, including knee examination of both knees
- Vital signs measurements (pulse rate, blood pressure, respiratory rate, and temperature)

- Venipuncture and collection of samples for clinical laboratory tests and biomarker analysis

Week 12

The Week 12 visit should occur on Day 85 (with a window of \pm 3 days). Subjects should fast for 8 hours prior to this visit.

The following procedures and assessments will be performed at this visit:

- Collection of AE and concomitant procedures/medication data
- Physical examination, including knee examination of both knees
- Vital signs measurements (pulse rate, blood pressure, respiratory rate, and temperature)
- Venipuncture and collection of samples for clinical laboratory tests and biomarker analysis
- qCT of both knees

Week 24

The Week 24 visit should occur on Day 169 (with a window of \pm 3 days). Subjects should fast for 8 hours prior to this visit. Prior to study medication injection, the Investigator should evaluate the subject for suitability to receive the second injection (refer to [Section 6.1.9](#)). The injection may occur up to two weeks later than the Week 24 visit to allow for resolution of any intercurrent illness (e.g., infection) prior to the injection. The subject should complete all other Week 24 assessments and return for an unscheduled visit and injection in the case that they are not able to receive the injection at the Week 24 visit.

The following procedures and assessments will be performed at this visit:

- Collection of AE and concomitant procedures/medication data
- Physical examination, including knee examination of both knees
- Vital signs measurements (pulse rate, blood pressure, respiratory rate, and temperature)
- Weight measurement
- Venipuncture and collection of samples for clinical laboratory tests and biomarker analysis
- Radiograph – bilateral in weight-bearing fixed flexion position, posterior-anterior (PA) view X-ray
- qCT of both knees
- DXA of the spine and hips
- Intra-articular study medication injection (or placebo)

Note: The Week 24 WOMAC and Patient Global Assessment must have already been completed prior to the Week 24 study medication injection.

Week 36

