10.3 Clinical Laboratory Evaluations

All chemistry, hematology and urinalysis results from the central laboratory will be comprehensively summarized into shift tables as normal, non-clinically significant abnormal, and clinically significant abnormal. Assessments of clinical significance for abnormal values were made by the investigator on results that were outside of the normal range. Comprehensive shift tables will compare the number and percent of assessments from each visit to baseline values for each treatment group.

All chemistry and hematology results from the central laboratory will be comprehensively summarized for each treatment group. Descriptive statistics of each laboratory test at all

timepoints will be provided along with the change from baseline at each subsequent timepoint for subjects in the SAS. The International System of Units (SI) will be used for all summaries.

Abnormal chemistry, hematology, urinalysis, and urine microscopy results for each subject will be provided in listings that will include laboratory test name, result, normal range, and an explanation for clinically significant values.

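### Laboratory and vital-sign values from unscheduled visits get no by-arm table, and the unqualified exclusion in SAP 8.1 should be limited to by-visit summaries

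*SAP*

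**What the plan says.** SAP 8.1 (General Statistical Methodology) gives the rule without exception: "Data collected from unscheduled visits will not be included in summary tables". The same sentence leaves such data to the listings, where appropriate. The paragraph before it deals with by-visit description: "For continuous variables, the outcome measure at each visit, as well as the absolute change". The rule itself stands in the following paragraph, with the provisions on listings, and no later section qualifies it.

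The protocol uses unscheduled visits for two purposes. Under Protocol 7.1.1, "The subject may be asked to return to the site for an unscheduled visit if an AE occurs between study visits" and the Investigator thinks a visit is needed to evaluate it fully. Under Protocol 7.3.3 the subject is to "return for an unscheduled visit and injection in the case that they are not able to receive the injection at the Week 24 visit". Protocol 7.3.4 and 7.3.5 say the same for the Week 52 and Week 76 injections.

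On tabulation, SAP 10.3 says of laboratory results: "Comprehensive shift tables will compare the number and percent of assessments from each visit to baseline values for each treatment group". It also plans descriptive statistics and change from baseline at each timepoint. SAP 10.2 gives vital signs at baseline and as change from baseline at each later visit. SAP 10.1 tabulates all AEs by unique subject over the whole study and separately for Phase B. SAP 14.2 says of exposure: "A summary table of the number injections received will be provided".

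**The concern.** Safety and tolerability through Week 52 is the primary objective, and safety from Week 52 to Week 104 falls under the third secondary objective. Vital signs and clinical laboratory measures are named safety endpoints in both phases.

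Unscheduled visits are not a random sample of time. One called to evaluate an AE happens because the subject is unwell. If values taken then are kept out of every table, the by-arm laboratory and vital-sign summaries rest only on measurements made on planned days. A change that appears and resolves between planned visits leaves no numerical trace in them. The likely direction is toward fewer abnormalities, although the documents contain nothing that would measure this. Listings show individual cases but do not compare the arms.

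Separately, a rule covering all data and all summary tables leaves a programmer to guess whether it reaches AE records and injection counts.

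**Working it through.** The plan gives no figure on this point to reproduce. The check is a comparison of sections plus one piece of date arithmetic.

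**1. Interval to the next scheduled visit after each injection** (nominal days from Protocol 7.3.3 to 7.3.5 and the Schedule of Events; injection given at the scheduled visit)

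| Injection | Next visit | Gap |
|---|---|---|
| Day 1 | Week 4, Day 29 | 29 − 1 = 28 days |
| Week 24, Day 169 | Week 36, Day 253 | 253 − 169 = 84 days |
| Week 52, Day 365 | Week 64, Day 449 | 449 − 365 = 84 days |
| Week 76, Day 533 | Week 88, Day 617 | 617 − 533 = 84 days |

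An injection deferred by the full two weeks, with the next visit on its nominal day, leaves 84 − 14 = 70 days. Either way, after the repeat injections any on-site measurement in that interval comes from an unscheduled visit.

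**2. Route of a laboratory or vital-sign value taken at such a visit**

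- By-visit tables (SAP 10.2, 10.3): excluded by SAP 8.1.
- Worst post-baseline or any-time table: none is planned.
- Listings: yes, as appropriate under 8.1. The laboratory listing in 10.3 covers abnormal results.
- AE tables: only if the Investigator judges the value abnormal and clinically significant. Protocol 7.1.1 (vital signs) and 7.2.1 (laboratory) then call for an AE record when the finding follows injection, and neither limits this to scheduled visits.

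Two things have no by-arm summary: values not judged clinically significant, and the numerical size and shift category of those that are. A clinically significant result found at an unscheduled visit could be counted as an AE and still be absent from the clinically significant column of the shift table.

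**3. AE and injection-count tables against 8.1**

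- SAP 10.1 treats AEs as events occurring over the study, not as visit measurements. Protocol 7.1.1 also has subjects asked at each study visit "for any continuing AEs or new AEs since the previous visit", so an event first seen between visits is covered again at the next one.
- SAP 14.2 counts injections received, with no limit by visit type. Membership of the Phase B full and safety sets (SAP 7.2, 7.7) also depends on receipt of an injection.
- If 8.1 were applied literally to exposure, each deferred injection would lower a count by one, for example 4 − 1 = 3 for a fully dosed subject. A subject with both Phase B injections deferred would belong to the Phase B safety set and yet show 2 − 2 = 0 Phase B injections. That is incoherent, which is itself evidence that 8.1 was not meant to reach this table.

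**The case against.** The strongest reply is that 8.1 is an ordinary by-visit rule. Keeping symptom-driven measurements out of by-visit means and shifts avoids mixing them with planned ones, and that reasoning is sound for those summaries. The specific sections on AEs and exposure should govern their own tables. A deferred injection displaces no assessments, because the subject completes everything else at the scheduled visit. Clinically significant laboratory and vital-sign findings become AEs and so reach by-arm tables. Protocol 7.1.1 does not say that blood is drawn or vital signs taken when a subject returns for AE evaluation.

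Most of this stands. A reader might infer from 8.1 that AEs and deferred injections will be missing from the safety and exposure tables. The documents do not support that, for the reasons in step 3 of the working. A reader might also extend the point to repeat scans, but neither document classes a post-baseline re-scan as an unscheduled visit. Nor is it shown that the excluded values would be the worst ones.

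The reply does not dispose of the rest. The AE route depends on a case-by-case clinical judgment, whereas shift tables and change summaries exist to reveal differences between arms that no single case would flag. As for whether such values exist, the 8.1 sentence itself provides for data from unscheduled visits, and Protocol 7.1.1 has vital signs measured at all visits except Screening Visit 2.

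**Conclusion.** The concern holds for laboratory and vital-sign values. Under SAP 8.1, 10.2 and 10.3, any such value measured at an unscheduled visit has no by-arm tabulation unless it is judged clinically significant and reported as an AE. The intervals most relevant to repeat dosing are the nominal 84 days after the Week 24, 52 and 76 injections.

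For AEs and injection counts the finding is narrower. The natural reading uses all records, and the fault is an unqualified sentence that conflicts with SAP 10.1 and 14.2 if taken literally.

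The size in subjects is unknown, because neither document gives the number of unscheduled visits, what was measured at them, or how often injections were deferred. The conclusion assumes only that some laboratory or vital-sign values were recorded at unscheduled visits. It concerns this SAP, whose laboratory and vital-sign tables run from baseline in the full Safety Analysis Set. The separate Phase A SAP is not among the documents, so whether it adds a worst-value summary cannot be checked.

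**What to change.** 1. In SAP 8.1, limit the exclusion to by-visit descriptive summaries.
2. State there that AE, concomitant medication, exposure and analysis-set derivations use all records whatever the visit type.
3. In SAP 10.3, add a worst post-baseline row by arm to the laboratory shift tables, using scheduled and unscheduled results.
4. In SAP 10.2, add minimum and maximum post-baseline rows by arm for vital signs, on the same basis.

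The cost is two sentences and a few table rows built from data already collected. The drawback is unequal ascertainment: subjects seen more often have more chances to show an abnormal value, so a difference between arms in visit frequency could produce a difference in the new rows. A footnote should say so. The by-visit tables stay as planned, so the reader has both views.
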